#### 9.4.5 Procedures for Handling Missing Serum Phosphorus Data

In the completed clinical study TEN-02-201 (with similar study design and primary efficacy variable but different treatment durations) conducted by Ardelyx, the rate of missing s-P data was 6.25% (5/80) at both week-2 and week-4 during the 4-week randomized withdrawal period. The rate of missing s-P data during the randomized withdrawal period in the current study is expected to be in the similar range for the first 4 weeks and higher than 6.25% thereafter (i.e., from week-4 to week-12, no information about such data from literature or other similar clinical trials). Since the last observation carried forward (LOCF) method (stated below) will be used for the primary efficacy analysis, the missing s-P data during the randomized withdrawal period is expected to have very limited impact on the power of the analysis for the current study.

An endpoint visit for the primary efficacy analysis is defined as the last visit with an s-P assessment during the randomized withdrawal period, which amounts to imputing the missing s-P data at Week-12 of the randomized withdrawal period using the LOCF method such that each patient's s-P value at the endpoint visit represents the patient's last experience while receiving study treatment. Assuming that more placebo patients will drop out early because of a lack of efficacy during the randomized withdrawal period, and as such, LOCF will tend to underestimate the true effect of the drug relative to placebo providing a conservative estimate of the drug's effect.

To support the primary efficacy analysis (LOCF method), a sensitivity analysis will be performed using a mixed-effects model for repeated measures (MMRM). Specifically, the dependent variable for the MMRM model will be the change in s-P from the end of the 26-week treatment period (Visit 13) to each visit during the 12-week randomized withdrawal period, and the MMRM model includes fixed effects of treatment, pooled investigator site, visit (Visit 14 through Visit 19), treatment-by-visit interaction, and the baseline s-P value as a continuous covariate. The baseline is defined as the s-P value at the end of 26-week treatment period. The covariance matrix for the repeated measures will be assumed to be unstructured. Within the framework of this model, the difference between the tenapanor treatment and placebo treatment in the mean change from the end of the 26-week treatment period to week-12 of the 12-week randomized withdrawal period will be estimated. The corresponding two-sided 95% CI and the p-value for the treatment difference will also be presented.

An endpoint visit (the LOCF method) will also be used for other efficacy analyses, if applicable. All other efficacy analyses will be performed based on the observed data.

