Patients who meet all the inclusion/exclusion criteria will be randomized 3:1 to either receive tenapanor at a dose of 30 mg bid or sevelamer carbonate based on package insert instructions (standard of care) after Visits 2, 3 or 4 (after 1, 2 or 3 weeks of wash-out) if they have a s-P level of at least 6.0 mg/dL and not more than 10.0 mg/dL and have an increase in s-P of at least 1.5 mg/dL versus pre wash-out (Visit 1, Screening visit).

Patients randomized into the tenapanor group will receive tenapanor at a dose of 30 mg bid. Tenapanor will be taken twice daily; just prior to breakfast and dinner. Patients on HD should **not** take tenapanor at the meal immediately preceding dialysis; in this case, patients will take tenapanor prior to the next meal after dialysis. Those randomized into the active control group will take sevelamer carbonate based on standard of care using the package insert for guidance for the entire 52-week study period. Patients who are on active control will **not** have Visits 14, 16 and 18.

Investigators may decrease or increase the dose of tenapanor based on s-P levels and/or GI tolerability. The changes must be made in 10 mg increments to a minimum of 10 mg bid or a maximum of 30 mg bid from enrollment until Day 183 (Visit 13). The dose of sevelamer carbonate may be adjusted based on standard of care for the entire 52-week study period.

During the 26-week treatment period and the safety extension period, patients on tenapanor with a s-P  $\geq$  10 mg/dL at any time after Week 2 of treatment or patients with a s-P  $\geq$  9 mg/dL for two consecutive visits after Week 2 will be discontinued and all visit procedures for Visit 23 will be completed, if possible. Patients in the active control group, receiving sevelamer carbonate do not have specific discontinuation criteria; they will be treated based on standard of care using the package insert for guidance.

At the end of the 26-week treatment period, patients in the tenapanor group only will be randomized 1:1 to either remain on the tenapanor dose they are taking on Day 183 (Visit 13) or receive placebo for up to an additional 12 weeks (randomized withdrawal period). During the randomized withdrawal period, patients with a s-P  $\geq$  9 mg/dL will be discontinued and all visit procedures for Visit 23 will be completed, if possible. Patients who discontinue from the

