### 5.4 Patient Withdrawal

Patients are free to discontinue the study at any time, for any reason, and without prejudice to further treatment. The Investigator may remove a patient if, in the Investigator's judgment, continued participation would pose unacceptable risk to the patient or to the integrity of the study data. Some study specific discontinuation criteria will also apply to study participants receiving tenapanor or placebo:

- **Hypophosphatemia:** Serum phosphorus  $\leq 2.5$  mg/dL at any time.
- **Hyperphosphatemia:**
  - Serum phosphorus  $\geq 10.0$  mg/dL any time after Week 2 of the 26-week treatment period
  - Serum phosphorus  $\geq 9$  mg/dL for two consecutive visits after Week 2 during the 26-week treatment or safety extension period
  - Serum phosphorus  $\geq 9$  mg/dL during the randomized withdrawal period

Patients discontinued from the randomized withdrawal period will be offered the opportunity to enter the open-label safety assessment period or be discontinued from the study and return to standard of care.

Patients in the active control group, receiving sevelamer carbonate do not have specific discontinuation criteria; they will be treated based on standard of care using the package insert for guidance.

A patient who discontinues will always be asked about the reason(s) for discontinuation and the presence of any AEs. The Investigator will record the reason for early withdrawal in the eCRF.

If a patient discontinues the study, all visit procedures for Visit 23 will be completed, if possible.

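### The supporting MMRM has no baseline-by-visit term, so its Week 12 contrast can be slightly biased if the link between Visit 13 and later s-P changes over time

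*Combined protocol and SAP*

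**What the plan says.** Section 9.4.5 supports the primary LOCF ANCOVA with a repeated-measures model of change in s-P from Visit 13. On the fixed effects: "the MMRM model includes fixed effects of treatment, pooled investigator site, visit (Visit 14 through Visit 19), treatment-by-visit interaction, and the baseline s-P value", the last as a continuous covariate. Baseline is Visit 13: "The baseline is defined as the s-P value at the end of 26-week treatment period". On the covariance: "The covariance matrix for the repeated measures will be assumed to be unstructured". The estimate of interest is tenapanor minus placebo at Week 12. No baseline-by-visit term is listed there or elsewhere in the text reviewed.

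Exit is tied to the outcome. Section 5.4 introduces its limits with "Some study specific discontinuation criteria will also apply to study participants receiving tenapanor or placebo". They include s-P of 2.5 mg/dL or less at any time and s-P of 9 mg/dL or more "mg/dL during the randomized withdrawal period". Under Section 4.1, patients who reach the upper limit in that period "mg/dL will be discontinued and all visit procedures for Visit 23 will be completed, if possible".

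Section 9.4.5 assumes more early dropout on placebo for lack of efficacy. It cites 6.25% missing s-P at Weeks 2 and 4 of an earlier study and expects a higher rate after Week 4.

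**The concern.** The treatment effect may vary by visit and the covariance is unrestricted, but the baseline slope is held constant from Week 2 to Week 12. When exit depends on observed s-P, a repeated-measures model gives a sound Week 12 contrast only if its mean model is right. Patients who leave for high s-P tend to have started higher at Visit 13, so observed and unobserved patients at Week 12 differ in baseline. A slope that is wrong at Week 12 then enters the predictions for those who left, by different amounts in the two arms.

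This is the only planned analysis that handles missing Week 12 s-P without carrying the last value forward. The per-protocol set in Section 9.3 requires completion of the 12 weeks, so it cannot do that job.

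**Working it through.** **Inputs from the documents.** Difference 1.0 mg/dL, SD 1.6 mg/dL, 73 per arm, two-sided 0.05, 560 patients randomized 3:1, 30% dropout, 50% responders (Section 9.2); exit limits (Section 5.4); model terms (Section 9.4.5).

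**Assumptions not in the documents.** Visit 13 mean 5.0 to 6.0 and SD 1.1 to 1.7 mg/dL, the within-patient correlations, and the speed of the placebo rise. Site effects were left out.

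**1. The plan's own figure.** SE = 1.6 × √(2/73) = 0.265. Power ≈ Φ(1.0/0.265 − 1.96) = Φ(1.82) = 96.5%; the exact noncentral t gives 96.3%. The stated power of more than 95% reproduces. Patient flow is 560 × 0.75 × 0.70 × 0.50 = 147, against 146. The documents give no figure for bias in the MMRM.

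**2. When the slope changes.** Regressed on Visit 13 s-P, the change to a later visit has slope ρ × (SD at that visit / SD at Visit 13) − 1. With equal SDs and correlation 0.9 per two-week step:
- Week 2: 0.9 − 1 = −0.10
- Week 12: 0.9⁶ − 1 = 0.53 − 1 = −0.47

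With a constant correlation of 0.5 the slope is −0.50 throughout, and a common slope is then correct.

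**3. Direction.** If the true slope steepens, the common slope is too shallow at Week 12. Predicted Week 12 change is then too high for patients who left with a high Visit 13 value. With more such patients on placebo, the placebo mean is pushed up and the contrast moves towards tenapanor. If the slope moves the other way, so does the bias.

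**4. Large-sample bias.** The runs used 100,000 to 120,000 patients per arm, a true effect of −1.0, and maximum likelihood with unstructured covariance. Exit was at either limit except where stated. Bias is in mg/dL; negative favours tenapanor.

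| Setting | Planned model | With baseline-by-visit |
|---|---|---|
| Autoregressive, 0.9 per step | −0.03 to −0.12 | within ±0.006 |
| Random intercept + autoregression + error, Visit 13 SD 1.5 | −0.02 to −0.07 | within ±0.006 |
| Responder-selected Visit 13 values | −0.02 to −0.04 | within ±0.006 |
| Exit at 9 or above only | −0.01 to −0.05 | within ±0.006 |
| Constant slope, −0.50 at all visits | 0.00 | 0.00 |
| No treatment effect | 0.00 | not needed |
| Constructed reversal: slope −0.50 at Week 2, −0.10 at Week 12 | +0.08 | 0.00 |

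The largest value seen was −0.18, with an SD of change of 2.07, above the planned 1.6. A further set at a true effect of about −1.0 gave −0.05 to −0.09 for the planned model and 0.005 or less with the term. Runs with a true difference near 1.30 and exit at 9 only gave overstatements of 1.317 − 1.299 = 0.018, 1.326 − 1.292 = 0.034 and 1.319 − 1.296 = 0.023.

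**5. At trial size.** In 600 trials of 73 per arm the mean estimates were −1.049 as planned and −0.998 with the term. The paired difference was −0.051 (Monte Carlo SE 0.002). The empirical SD of the planned estimate was 0.244, so the shift is 0.051/0.244 = 0.2 standard errors. Coverage of a 95% interval becomes about Φ(1.76) − Φ(−2.16) = 94.5%.

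**6. Slopes that differ by arm.** Here placebo loses a patient-specific drug effect, and the true effect was −1.0 to −1.5. With exit at 9 only, the planned model was off by −0.023 to −0.081 and the model with the term by −0.022 to −0.056. With both exit limits, the planned model was off by −0.003 to −0.105 and the model with the term by −0.018 to +0.011.

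**The case against.** A common baseline slope is a recognised MMRM form, and the plan does not contradict itself here. The documents give no visit-to-visit correlations, so a slope that changes with time is assumed, not shown. The size is about 0.2 standard errors at most trial-size settings examined, and there is no bias without a treatment effect. The model is outside the testing sequence of Section 9.4.4.1. The term may also be incomplete, because differing slopes are plausible when one arm stops drug. All of this stands and limits the weight of the point. None of it favours the common slope: when the arms share slopes, the wider model is right whether the slope is constant or changing, and the planned one only if it is constant.

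Section 9.1 says a separate SAP governs where it differs. No such separate text was available in the documents reviewed. If it already includes the term, the point falls away.

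Three stronger readings are tempting.
- A reader might infer that the MMRM necessarily favours tenapanor. The documents do not support this, since the direction depends on how the baseline link evolves.
- A reader might infer that responders are chosen for a low Visit 13 value. Sections 9.3 and 9.4.3 require a fall of at least 1.2 mg/dL from Day 1, with no ceiling at Visit 13. As entry is allowed up to 10.0 mg/dL (Section 5.1), a Visit 13 value of 8.8 can still qualify.
- A reader might take heavier placebo exit as established. Section 9.4.5 offers it as an assumption, and in some of the runs in step 6 with both limits, total exit was slightly higher on tenapanor.

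**Conclusion.** The point holds as a conditional and minor one. One Visit 13 slope across six visits, with exit driven by s-P, leaves the Week 12 contrast open to bias if the baseline link changes over time. If the link weakens, as is usual for a repeated laboratory value, the bias is towards tenapanor. It is about 0.01 to 0.12 mg/dL for a true difference near 1.0 and an SD of change near 1.6, and 0.02 to 0.04 in the responder-selected runs, which are closest to the primary population. These sizes rest on assumed correlations, Visit 13 distributions and placebo trajectories. The bias creates no false positive by itself and leaves the primary test untouched. What it weakens is the MMRM's value as a check on LOCF, which Section 9.4.5 presents as conservative.

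**What to change.** Before unblinding, add the baseline s-P-by-visit interaction to the MMRM fixed effects in Section 9.4.5, and in the separate SAP if it repeats the list. With six visits this costs five parameters, which about 146 patients can bear; in the trial-size runs the SD of the estimate was 0.234 with the term and 0.244 without. No other part of the plan needs to change. If the team expects baseline slopes to differ between continued drug and placebo, it can specify arm-specific baseline-by-visit slopes, with the contrast evaluated at the overall mean baseline, because the simple interaction may then leave up to about 0.06 mg/dL.

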#### 9.4.6 Methods of Pooling Data

For the purpose of adjusting for investigator effects in statistical models, investigator sites will be pooled into groups based on geographic region and number of patients enrolled with

an aim for comparable sample sizes among pooled investigator sites. The goal of the pooling strategy will be to avoid less than a minimum number of patients per pooled investigator site. The size of a pooled investigator site would generally depend on the enrollment size for each individual investigator site. The pooled investigator sites will be used in all applicable analyses where adjustment for investigator effect is desired.

#### 9.4.7 Visit Windows

No analysis visit windows will be formally defined. The schedule of events in [Section 1.3](#) details the intended collection of study variables at specified visits. Should additional data be collected between scheduled visits, these data will be included in the patient data listings but ignored for analyses purposes, unless the additional data is the last data collected during each study period.

#### 9.4.8 Safety Analyses

Safety analyses include summaries for adverse events, safety laboratory tests, vital signs, body weights, 12-lead ECGs, and physical examinations. These summaries will be provided for each study period separately.

Adverse events will be coded using the Medical Dictionary for Regulatory Activities (MedDRA). Summary tables and listings will be provided by system organ class and preferred term for each treatment (including dose, if applicable) group for treatment-emergent adverse events (TEAEs). Actual values and change from baseline values for clinical laboratory tests, vital signs, body weights, and ECGs will be summarized by treatment (including dose, if applicable) group for each visit. The number and percentage of patients in each physical examination category will be presented by treatment (including dose, if applicable) group for each visit.

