#### **3.2 Secondary Objectives**

The secondary objectives of this study are:

- To compare the phosphorus lowering effect between tenapanor and placebo based on the change in serum phosphorus (s-P) from the end of the 26-week treatment period to the end of the randomized withdrawal period or the endpoint visit for this period in the intent-to-treat (ITT) analysis set and at individual doses of tenapanor and placebo in both the efficacy and ITT analysis sets.
- To evaluate the effect of tenapanor on the change in serum phosphorus levels from baseline to the end of 26-week treatment period
- To evaluate the effect of tenapanor on the number of patients reaching serum phosphorus goal levels defined as < 5.5 mg/dl during the 26-week treatment period.
- To evaluate the effect of tenapanor on Calcium- Phosphorus Product (Ca x P) during all three study periods (26-week treatment period, randomized withdrawal period and safety extension period).
- To evaluate the effect of tenapanor on intact fibroblast growth factor 23 (iFGF23) and c-terminal FGF23 (cFGF23) levels during all three study periods (26-week treatment period, randomized withdrawal period and safety extension period).
- To evaluate the effect of tenapanor on the Kidney Disease Quality of Life (KDQoL) survey during all three study periods.
- To evaluate the effect of tenapanor on the Dialysis Symptom Index (DSI) survey during all three study periods (for English speakers only).
- To compare the long-term safety of tenapanor to the active control sevelamer carbonate.

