**8.9 Randomized Withdrawal Period (Days 197, 211, 225, 239 and 253 ± 7), Visits 14, 15, 16, 17 and 18**

**Subjects in the active control group do not have Visits 14, 16 and 18.**

- Vital signs (pre-dialysis)
- Serum phosphorus (pre-dialysis)
- FGF-23, Ca x P product and exploratory biomarker sample (Days 211 and 239 ± 5, Visits 15 and 17 only)
- Dispense study drug or active control at Visits 15 and 17 only, if applicable
- Return/accountability of study drug or active control
- Adverse event reporting
- Review concurrent medications

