### **9.2 Determination of Sample Size**

Approximately five hundred sixty (560) male and female patients with end stage renal disease (ESRD) on chronic maintenance hemodialysis (HD) 3 times a week for a minimum of 3 months or peritoneal dialysis (PD) for a minimum of 6 months will be enrolled in this study. Patients will be randomized in a 3:1 ratio to receive either tenapanor (~420 patients) or active control (~140 patients). Those patients in the tenapanor group will be randomized at the end of the 26-week treatment period to enter into the randomized withdrawal period to either remain on their current dose of tenapanor or placebo in a 1:1 ratio.

For the primary efficacy analysis, a sample size of 146 patients (73 patients/group) in the 12-week randomized withdrawal period is expected to provide more than 95% power to detect a difference between tenapanor and placebo treatment in the change in serum phosphorus from the end of the 26-week treatment period to the end of the 12-week randomized withdrawal period or the endpoint visit for this period, between the tenapanor treatment and placebo. This calculation is based on a two-sample t-test with a two-sided significance level of  $\alpha=0.05$ , an assumed treatment difference of 1.0 mg/dL and a common standard deviation of 1.6 mg/dL. This sample size (560) allows for a 30% dropout rate, meaning 30% of patients will not complete the 26-week treatment period. This sample size also assumes at least 50% of patients in the tenapanor group will be considered responders in the 26-week treatment period, i.e., patients who achieves at least a 1.2 mg/dL reduction from baseline to the end of the 26-week treatment period.

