**Safety Analysis Set:**

All patients who receive at least one dose of study drug (tenapanor or placebo) or active control for the individual study period will be included in the safety analysis set. Such patients will be analyzed according to the treatment actually received.

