**9.4 Statistical Methods**

**9.4.1 General Approach**

Descriptive statistics including the number of observations, mean, standard deviation, median, minimum, and maximum will be presented for continuous variables. Frequency and percentage of patients will be presented for categorical variables. Continuous variables will be analyzed using analysis of variance (ANOVA) or analysis of covariance (ANCOVA). Categorical variables will be analyzed using a Cochran-Mantel-Haenszel (CMH) test or a Pearson's Chi-square test.

Safety analyses will be performed on all patients enrolled in this study, while efficacy analyses will be performed only on those patients who are randomized to receive tenapanor

in the 26-week treatment period (i.e., patients treated with active control will not be included in any efficacy analyses).

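### The protocol sets a long-term safety comparison with sevelamer but gives it no between-arm or exposure-adjusted measure, so its crude by-period percentages could mislead in either direction.

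*Combined protocol and SAP*

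**What the plan says.** Section 3.1 makes safety and tolerability over up to 52 weeks a primary objective. Section 3.2 adds a comparative one: "To compare the long-term safety of tenapanor to the active control sevelamer carbonate". Section 4.1 gives safety as the reason for the sevelamer arm, and Section 9.4.1 keeps that arm out of every efficacy analysis. About 140 patients therefore serve this one comparison.

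The planned outputs are these:
- Section 9.4.8, on AEs: "Summary tables and listings will be provided by system organ class and preferred term for each treatment (including dose, if applicable) group".
- Section 9.4.8, on all safety outputs: "These summaries will be provided for each study period separately".
- Section 9.4.1: "Frequency and percentage of patients will be presented for categorical variables". It also mentions CMH and chi-square tests in general terms, without tying them to AEs.
- Section 9.3 limits each period's safety set to patients who had "at least one dose of study drug (tenapanor or placebo) or active control for the individual study period", analysed by treatment actually received.

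The arms are handled differently:
- Section 5.4 applies serum-phosphorus discontinuation rules to patients on tenapanor or placebo. Section 4.1 says: "Patients in the active control group, receiving sevelamer carbonate do not have specific discontinuation criteria".
- Section 9.2 allows for 30% dropout, "meaning 30% of patients will not complete the 26-week treatment period", without splitting it by arm.
- At Visit 13 tenapanor patients are re-randomised 1:1 to tenapanor or placebo. Section 4.1.1 says control patients do not enter that period.
- Footnote g of the Schedule of Events (Section 1.3) lets patients move to the extension at any withdrawal-period visit.
- Section 8.9: "Subjects in the active control group do not have Visits 14, 16 and 18".

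Section 9.1 says that a separate SAP governs where it differs from the protocol, and that no changes to the primary and secondary analyses are expected.

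**The concern.** A percentage of patients with an event depends on how long, and how often, patients are observed. If one arm is followed for less time, it shows fewer patients with events at the same true rate. After Week 26 the tables also cover only patients who remained. They left under different rules in the two arms, so the later comparisons are no longer protected by randomisation. The protocol offers nothing to set against this: no contrast between the arms as first randomised, no interval, no rate per unit of exposure and no time-to-event display. It also does not say which calendar interval counts as the withdrawal or extension period for a sevelamer patient. At stake is the answer to a stated objective, and the whole yield of the control arm.

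**Working it through.** **The plan's own figures.** The protocol states no figure for the safety comparison. Its sample size arithmetic does reproduce: 420 × 0.70 × 0.50 = 147, against the stated 146. This uses the 30% for the tenapanor arm and says nothing about sevelamer dropout, which is therefore varied below.

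**The 26-week table, equal true rates.** Assumptions: the same constant event rate λ in both arms; a fraction p of an arm leaves evenly over T = 26 weeks; a true 52-week risk of 50%, so λT = ½ ln 2 = 0.3466.

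- Risk if followed for 26 weeks: 1 − e^(−λT) = 0.2929.
- Average risk observed in a patient who leaves: 1 − 0.2929/0.3466 = 0.1549.
- Crude percentage: (1 − p) × 0.2929 + p × 0.1549.
- Mean follow-up: 26 × (1 − p/2) weeks.

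Tenapanor at p = 0.30: 0.2050 + 0.0465 = 25.1%, with mean follow-up of 22.1 weeks.

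| Sevelamer dropout | Mean follow-up (weeks) | Sevelamer crude % | Tenapanor crude % | Ratio (truth 1.00) |
|---|---|---|---|---|
| 0% | 26.0 | 29.3 | 25.1 | 0.86 |
| 10% | 24.7 | 27.9 | 25.1 | 0.90 |
| 20% | 23.4 | 26.5 | 25.1 | 0.95 |
| 30% | 22.1 | 25.1 | 25.1 | 1.00 |

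With a constant rate, events divided by event-free time at risk estimates λ in both arms, so the exposure-adjusted ratio is 1.00 in every row.

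**Other dropout and event patterns.** With exponential dropout at rate δ, the crude risk is λ/(λ + δ) × (1 − e^(−(λ+δ)T)). For a 26-week risk of 20% and 30% tenapanor dropout, λT = 0.223 and δT = 0.357, which gives 16.9%. Sevelamer gives 20.0, 19.0, 18.0 and 16.9% at 0, 10, 20 and 30% dropout: ratios of 0.85, 0.89, 0.94 and 1.00. Over base risks of 5 to 40% the ratio runs from 0.84 to 1.00. If 90% of events fall in the first two weeks, with sevelamer dropout of 10%, the figures are 19.4% and 19.8%: a ratio of 0.98.

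**After Week 26, forces favouring tenapanor.**
- *Selection (shares assumed).* Let 25% of patients be susceptible, with a period risk of 40% against 10% for the rest. The expected risk is 0.25 × 0.40 + 0.75 × 0.10 = 17.5%. If early losses leave 5 to 15% susceptible on tenapanor but 25% on sevelamer, tenapanor shows 11.5 to 14.5%: ratios of 0.66 to 0.83.
- *Time on drug.* A patient who goes tenapanor, placebo, tenapanor and completes has 26 + 14 = 40 weeks on drug, against 52 on sevelamer.

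**After Week 26, forces against tenapanor.**
- *Ascertainment.* In the withdrawal period AEs are asked about at six visits (14 to 19) on tenapanor or placebo, and at three (15, 17, 19) on sevelamer.
- *Early extension entry.* Visit 19 to Day 365 is (365 − 267)/7 = 14 weeks. Entry at Visit 14 gives (365 − 197)/7 = 24 weeks. With a 14-week risk of 10%, the 24-week risk is 1 − 0.9^(24/14) = 16.5%. If 10% enter then and stay to Day 365, the group shows 0.9 × 10.0 + 0.1 × 16.5 = 10.65%. For shares of 10 to 30% and base risks of 10 to 20%, the ratio is 1.06 to 1.20.
- *Recording.* Section 7.3.5 makes an AE of an out-of-range laboratory value that the investigator considers clinically significant and that requires discontinuation. Only tenapanor and placebo patients have phosphorus rules that can trigger this.

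**The case against.** Four points can be made for the plan.

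1. By-period reporting already does useful work. It fixes the nominal lengths at 26, 12 and 14 weeks and shows placebo as its own group, so placebo time does not dilute the tenapanor percentages in the withdrawal period. In the first 26 weeks both arms are as randomised. This stands: differential selection is a problem after Week 26 only, and by then the sevelamer patients are also those who remained.
2. Unequal dropout is not documented. The one-sided phosphorus rules make it plausible, but the protocol gives no size for it. This stands, and is why the table runs to equal dropout. Those rules also select on phosphorus control, not directly on tolerability.
3. Patient-year rates have their own weakness. If events come early, they flatter the arm followed for longer. This stands, and is why the rates need a time-to-event display beside them.
4. The separate SAP may already contain these analyses. This cannot be excluded. Section 9.1 expects no changes to the secondary analyses, which makes Section 9.4.8 the best available evidence of intent, but not proof.

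A reader might go further and infer that the plan tends to favour tenapanor. The documents do not support a direction: visit frequency, early extension entry and AE recording push the other way. A reader might also pool 52 weeks: with a true risk of 50%, 30% tenapanor dropout and no sevelamer dropout, the crude figures would be 0.7 × 50 + 0.3 × 15.5 = 40% against 50%. The protocol plans no such table, so that contrast does not measure a bias in its outputs.

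**Conclusion.** The concern holds for the protocol text. A stated comparative safety objective has no comparative method, and the planned by-period percentages can mislead in either direction.

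In the 26-week table the illustrated distortion is at most about four percentage points (25.1% against 29.3%), and that needs no sevelamer dropout at all. It vanishes with equal dropout and nearly vanishes when events cluster early. For scale, at a 20% risk in both arms the 95% interval for a difference between 420 and 140 patients has a half-width of 1.96 × √(0.16/420 + 0.16/140) = 7.7 points. The largest distortion at that risk is 20.0 − 16.9 = 3.1 points. It is smaller than the sampling error but systematic. After Week 26 the illustrated ratios run from 0.66 to 1.20, and those comparisons are among patients who remained in the study.

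The event rates, sevelamer dropout, susceptible shares and early-entry shares are assumptions, because the protocol gives none of them. That the sign depends on such unknowns is itself a reason to fix the method in advance.

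**What to change.** In Section 9.4.8, and in the SAP if it is not already there:

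1. Name the randomised 26-week period as the main safety comparison. Report risk differences with 95% confidence intervals, and Kaplan-Meier or cumulative incidence curves of time to first event, for key AEs, SAEs and discontinuations.
2. Add exposure-adjusted incidence rates to Week 52 by Randomization #1 arm, with placebo time separated from tenapanor time. Read them beside the time-to-event display, because they assume a roughly constant hazard.
3. Define the control arm's calendar periods after Week 26. Label later-period comparisons as descriptive, among patients who remained. Add a sensitivity analysis limited to AEs collected at visits common to both arms.

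The cost is a few more tables and figures from data already collected, with no change to visits or patient care. The one downside is the constant-hazard assumption behind the rates, which the paired display addresses.
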